6. DOSE MODIFICATIONS

If toxicity occurs, the toxicity will be graded using the NCI CTCAE Version 5.0, and appropriate supportive care treatment will be administered to decrease the signs and symptoms thereof. Dose adjustments will be based on the organ system exhibiting the greatest degree of toxicity.

Doses of patritumab deruxtecan will be modified based on hematologic and non-hematologic toxicity. If dose reductions are necessary, they will be permanent for the remainder of the treatment. Any patient requiring a toxicity-related dose delay of more than 18 weeks (126 days) from the last patritumab deruxtecan dose must be discontinued from the study, unless discussed with the Medical Monitor for extenuating circumstances. During the time of any dose delay, scheduled CT/MRI scans should continue as per protocol, and subjects should fulfill all of the following criteria:

- Study drug may be resumed with confirmation of continued benefit per RECIST 1.1. Scans should be performed at the frequency defined per protocol while the drug is being held.
- At minimum, 1 restaging scan must be done within 6 weeks prior to restarting the study drug.
- Investigational product is restarted within the guidance of the treatment management guidelines for patritumab deruxtecan, if appropriate.
- No prohibited concomitant medications have been administered since the last dose of patritumab deruxtecan.

If toxicities occur that are \leq Grade 2, they should be managed symptomatically, if possible, and the patient should be re-treated without a dose reduction. If toxicities occur that are \geq Grade 3, treatment should be withheld until resolution to \leq Grade 1 or to the baseline value (if the baseline value was $>$ Grade 1). Treatment should then be re-instituted, if medically appropriate, at the next lower dose level (see Table 2).

The dose level reductions to be used in this study are presented in Table 2.

CONFIDENTIAL

Table 2 Dose Level Modifications

Dose Level	Patritumab deruxtecan
Starting Dose	5.6 mg/kg
Dose Level -1	4.8 mg/kg
Dose Level -2	3.2 mg/kg

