6.2.1 Specific Recommendations for ILD

If a patient develops radiographic changes potentially consistent with ILD or develops an acute onset of new or worsening pulmonary or other related signs/symptoms, such as dyspnea, cough, or fever, rule out ILD.

If ILD is suspected, delay patritumab deruxtecan dosing pending further evaluation and start corticosteroid treatment promptly unless clinically contraindicated.

Evaluation must include CT (preferably high-resolution CT) and pulmonologist consultation (when the Investigator is not a pulmonologist). The following evaluations should also be obtained, as indicated:

- Infectious disease consultation as clinically indicated
- Blood cultures and CBC (other blood tests could be considered as needed)
- Bronchoscopy and bronchoalveolar lavage if clinically indicated and feasible
- Pulmonary function tests
- Pulse oximetry (peripheral capillary oxygen saturation [SpO₂])
- Arterial blood gases, as clinically indicated
- Diffusing capacity for carbon monoxide (DLCO), as clinically indicated
- One blood sample collection for PK analysis as soon as ILD is suspected, if feasible
- Other tests, as clinically indicated

If the AE is confirmed to be ILD, follow the management guidance outlined in Table 4. If a non-inflammatory/infectious etiology is confirmed by the Investigator, treat accordingly and resumption of patritumab deruxtecan may occur after discussion between the Investigator and Sponsor.

CONFIDENTIAL

All events of ILD regardless of severity or seriousness will be followed until resolution, including after drug discontinuation.

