10.4.3 Safety Analysis

All safety endpoints, including laboratory results, vital signs, and ECG findings, will be summarized for patients in the Safety Analysis Set.

Adverse Events

Safety will be assessed through the analysis of the reported incidence of treatment-emergent AEs. Treatment-emergent AEs are those with an onset on or after the initiation of therapy up to 40 days (+ 7 days) after last day of treatment and will be graded according to NCI CTCAE Version 5.0. Serious adverse events starting or worsening after the on-treatment period, if reported as related to the study treatment, are also TEAEs. The AE summary will include only TEAEs.

The AEs will be coded using the current version of Medical Dictionary for Regulatory Activities (MedDRA; <https://www.meddra.org/about-meddra/>) and summarized using system organ class and preferred term overall and by biomarker-defined subgroup for all patients in the Safety Analysis Set. In addition, summaries of SAEs, AEs leading to treatment discontinuation, AEs by maximum NCI CTCAE grade, and AEs related to study treatment will also be presented overall and by biomarker-defined subgroup.

Clinical Laboratory Tests

Descriptive statistics will be provided for clinical laboratory test results (hematology and chemistry) and changes from baseline by scheduled time of evaluation, including the EOT visit.

CONFIDENTIAL

Abnormal laboratory results will be graded according to NCI CTCAE Version 5.0, if applicable. A shift table, presenting the 2-way frequency tabulation for baseline and the worst on-treatment value according to the NCI CTCAE grade, will be provided for clinical laboratory tests. Abnormal clinical laboratory test results \geq Grade 3 will be listed.

Concomitant medications will be coded using the World Health Organization Drug Dictionary (WHO DD; <https://www.who-umc.org/>), and they will be listed and summarized by overall and by biomarker-defined subgroup.

Vital Signs

Descriptive statistics will be provided for the vital sign measurements and changes from baseline by scheduled time of evaluation, including the EOT visit.

Electrocardiogram Analyses

Descriptive statistics will be provided for ECG parameters and changes from baseline, including the EOT visit. In addition, the number and percentage of patients meeting the following criteria will be tabulated for QT and QTcF: ≤ 450 msec, >450 to ≤ 480 msec, >480 msec to ≤ 500 msec, and >500 msec, and change from baseline ≥ 30 msec and ≥ 60 msec.

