11.1.5 Recording and Reporting of Adverse Events

Recording of Adverse Events

All AEs of any patient during the course of the research study will be recorded in the eCRF, and the Investigator will give his or her opinion as to the relationship of the AE to the study drug treatment (i.e., whether the event is related or unrelated to study drug administration).

All AEs should be documented. A description of the event, including its date of onset and resolution, whether it constitutes an SAE or not, any action taken (e.g., changes to study treatment), and outcome, should be provided, along with the Investigator's assessment of causality (i.e., the relationship to the study treatment[s]). For an AE to be a suspected treatment-related event, there should be at least a reasonable possibility of a causal relationship between the protocol treatment and the AE. Adverse events will be graded according to the NCI CTCAE Version 5.0, and changes will be documented.

If the AE is serious, it should be reported immediately to Development Innovations Safety Department. Other untoward events occurring in the framework of a clinical study are to be recorded as AEs (i.e., AEs that occur prior to assignment of study treatment that are related to a protocol-mandated intervention, including invasive procedures such as biopsies, medication washout, or no treatment run-in).

Any clinically significant signs and symptoms, abnormal test findings, changes in physical examination, hypersensitivity, and other measurements that occur will be reported as AEs and collected on the relevant eCRF screen.

Test findings will be reported as an AE if: the test result requires an adjustment in the study drug(s) or discontinuation of treatment and/or test findings require additional testing or surgical intervention, a test result or finding is associated with accompanying symptoms, or a test result is considered to be an AE by the Investigator.

Reporting Period for Adverse Events

All AEs, regardless of seriousness or relationship to patritumab deruxtecan treatment (called study treatment), spanning from the start of study treatment until 40 calendar days (+7 days) after discontinuation or completion of study treatment as defined by the clinical study for that patient

CONFIDENTIAL

after his/her last dose of study drug, are to be recorded on the corresponding screen(s) included in the eCRF.

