All AEs resulting in discontinuation from the study should be followed until resolution or stabilization. All new AEs occurring during this period must be reported and followed until resolution unless, in the opinion of the Investigator, the AE or laboratory abnormality/ies is/are not likely to improve because of the underlying disease. In this case, the Investigator must record his or her reasoning for this decision in the patient's medical record.

After 40 days after completion of protocol-specific treatment or discontinuation, only AEs, SAEs, or deaths assessed by the Investigator as treatment-related are to be reported.

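### A late, related, non-serious ILD/pneumonitis is collected and can be adjudicated, but no planned safety summary would show it

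*Combined protocol and SAP*

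**What the plan says.** **Analysis rule (Section 10.4.3).** A treatment-emergent AE starts on or after first treatment and no later than 40 (+7) days "after last day of treatment and will be graded according to NCI CTCAE Version 5.0". There is one extension: "Serious adverse events starting or worsening after the on-treatment period, if reported as related to the study treatment, are also TEAEs". The next sentence reads: "The AE summary will include only TEAEs". The section then lists further summaries: SAEs, AEs leading to discontinuation of treatment, AEs by maximum grade, and related AEs. It lists none for adverse events of special interest, for ILD, or for the ILD committee's findings.

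**Collection rule (Sections 11.1.5 and 11.2.1).** All AEs are recorded "until 40 calendar days (+7 days) after discontinuation or completion of study treatment". After that, "only AEs, SAEs, or deaths assessed by the Investigator as treatment-related are to be reported". Section 11.2.1 repeats the later rule. Neither section asks that a late related AE be serious before it is reported.

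**ILD provisions.** Section 11.4 makes ILD/pneumonitis an adverse event of special interest. Section 11.4.1 sets up an independent adjudication committee, whose data collection starts when an AE is reported under a listed ILD or respiratory-failure term. Section 6.2.1 adds: "All events of ILD regardless of severity or seriousness will be followed until resolution, including after drug discontinuation".

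**The concern.** Collection and tabulation use different filters for late events. Collection asks whether the investigator judged the event related. Tabulation asks that and also whether it was serious. An event that passes the first filter and fails the second is held in the database but shown nowhere.

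For most toxicities this would hardly matter. ILD is different. Section 1.2 calls it an important identified risk, Section 6.2.1 requires follow-up whatever the seriousness, and a committee exists to review it. The committee could confirm a late case that the AE tables do not contain, and a reader of those tables would not know. Few related cases are likely in a trial of 121 patients, so a single omitted case would be noticeable.

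**Working it through.** There is no stated figure to reproduce, because the point concerns definitions and data flow. The check takes each type of ILD event with onset after the 40 (+7)-day window through the three rules.

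| Event with onset after the window | Must be reported (11.1.5, 11.2.1) | Can trigger adjudication (11.4.1) | In a planned AE summary (10.4.3) |
|---|---|---|---|
| Related, serious | Yes | Yes | Yes, through the extension |
| Related, non-serious | Yes | Yes | **No** |
| Judged unrelated, non-fatal | No | Only if reported anyway | No |

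The second row is the gap. It follows from the text and needs no numerical assumption. Section 6.2.1 does not close it, because it governs follow-up of ILD events and is silent on tabulation.

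**Which grades are affected.** Table 4 (Section 6.2) requires hospitalization for Grade 3 and 4 ILD, and hospitalization normally makes an event serious under Section 11.1.2. What remains is mainly Grade 1 and 2. Grade 2 is not trivial: Table 4 calls for permanent discontinuation and prompt systemic steroids.

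**Scale, from Study J101 (Section 1.1.3).**
- Treated patients: 144. Related pneumonitis or ILD events: 6 pneumonitis + 1 ILD = 7, and 7/144 = 4.9%.
- Grades of those 7: pneumonitis, 3 at Grade 2 and 3 at Grade 3; the ILD event, Grade 2. So 4 of 7 were Grade 2.
- Pneumonitis was an SAE in 3 patients. Assuming these are 3 of the same 6, non-serious pneumonitis = 6 − 3 = 3.
- The seriousness of the one ILD event is not given; the SAE list covers only terms seen in more than one patient. Non-serious related events are therefore 3 + 0 = 3 or 3 + 1 = 4, that is 3/7 = 43% or 4/7 = 57%.
- At the same rate, 121 patients would give 121 × 7/144 = 5.9 related treatment-emergent events.

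These figures show that related ILD is often non-serious. They do not say how many cases would start after the window. The J101 events are described as treatment-emergent, J101's own window is not stated, and no onset times are given.

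**The case against.** The best defence is that Section 10.4.3 separately promises a summary of AEs related to study treatment, and a late related ILD is such an AE. The sponsor may intend that. But the sentence limiting the AE summary to TEAEs comes first, and nothing exempts the related-AE table from it. If the wider reading is meant, it should be written down.

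It is also fair to say that these cases are not lost. They must be reported, they can trigger adjudication, and Section 11.1.2 lets an investigator classify an important medical event as serious. All of that stands, and it narrows the gap. It does not put a non-serious case into a table.

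Three stronger readings are tempting and are not supported:

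- **The toxicity hold opens a long blind period.** Section 6 provides that a patient with a "toxicity-related dose delay of more than 18 weeks (126 days) from the last patritumab deruxtecan dose must be discontinued", so one might count 126 − 47 = 79 days outside the window. That requires the last day of treatment to mean the last dose. Section 11.1.5 counts from discontinuation or completion, although it also mentions the last dose, and a patient on hold has not discontinued. On that reading, events during a hold are inside the window.
- **The number of omitted cases can be estimated.** One could assume a late share and multiply it by the J101 rate. The documents give no late share. Because the J101 events were themselves treatment-emergent, late cases could be additional to that rate and not a fraction of it. J101 also covered several doses and schedules. Any product of this kind would be neither an estimate nor an upper limit.
- **Late events judged unrelated should also have to be reported.** The third row of the table shows that they need not reach the committee. Related-only reporting after the window is a stated choice, however, and the causality guide in Section 11.1.6 favours a related call for a known drug effect. Follow-up after treatment is partial, and the direction of any effect is unknown. The documents do not show that this rule is wrong.

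**Conclusion.** The gap is real and narrow. A new ILD or pneumonitis starting after the 40 (+7)-day window, judged related and non-serious, is collected and can be adjudicated but is absent from every planned summary. Against the count of all reported investigator-related ILD, the tabulated count can be too low and cannot be too high. That says nothing about the count of truly drug-caused ILD, since investigator attribution can err either way.

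The conclusion rests on reading the TEAE restriction as covering all the listed AE summaries, which is the plain reading. The number of cases is probably small and cannot be estimated from the documents. No primary endpoint is affected. The change is an inexpensive improvement that the sponsor could make; the gap is not a flaw that threatens the trial's conclusions.

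**What to change.** Add to Section 10.4.3: *All reported ILD/pneumonitis, and all events adjudicated as ILD, will be summarized by grade regardless of seriousness or onset date, with onset within and after the 40 (+7)-day window shown separately.*

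The TEAE definition can stay as it is, so the standard AE tables do not change. Sections 11.1.5 and 11.2.1 need no change either, because the events in question are already reportable.

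The cost is one extra table, with no added visits, scans or forms. A footnote should say that ascertainment after the window is incomplete. Under Section 7.4.3, follow-up for progression applies to patients who stop without progressive disease, ends at subsequent treatment among other events, and may be done by record review every 3 months. The late-onset figures should therefore be read as a count of known cases and not as a rate.

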1.1.3 Clinical Safety

The safety and preliminary efficacy of patritumab deruxtecan were evaluated in the on-going Phase I/II Study U31402-A-J101 in US and Japan in patients with metastatic breast cancer (MBC). The trial enrolled advanced/unresectable MBC patients (irrespective of subtype) with HER3 positive tumors who were refractory/intolerant to standard therapy in the dose escalation

CONFIDENTIAL

phase. Patients with HER3-positive MBC who had received ≥ 2 and ≤ 6 prior chemotherapy regimens were then enrolled in the dose-finding phase and subsequent expansion phase. The expansion phase included HR+/HER2- and triple negative MBC patients with HER3 high expression and HR+/HER2- MBC patients with HER3 low expression. Two different doses of patritumab deruxtecan, 4.8 mg/kg and 6.4 mg/kg, were evaluated.

As of the data cut-off date of 05 August 2019, 144 of 145 patients enrolled in Study U31402-A-J101 had received patritumab deruxtecan: 34 patients in the dose escalation part, 32 patients in the dose-finding part, and 78 patients in the dose expansion part. A total of 141 (97.9%) patients had experienced at least 1 treatment-emergent adverse event (TEAE) and 138 (95.8%) patients had experienced at least 1 TEAE considered related to study drug by the Investigator. The most frequent TEAEs (in $>20\%$ of patients), all grades, regardless of causality and noted in descending order of frequency, included nausea (113 [78.5%] patients), decreased appetite (74 [51.4%] patients), platelet count decreased (65 [45.1%] patients), neutrophil count decreased (61 [42.4%] patients), vomiting (57 [39.6%] patients), white blood cell count decreased (53 [36.8%] patients), anemia (52 [36.1%] patients), diarrhea (50 [34.7%] patients), aspartate aminotransferase (AST) increased (41 [28.5%] patients), fatigue (40 [27.8%] patients), alanine aminotransferase (ALT) increased (36 [25.0%] patients), stomatitis (36 [25.0%] patients), constipation (32 [22.2%] patients), and alopecia and malaise (31 [21.5%] patients each).

There were 92 (63.9%) patients with TEAEs of Grade 3 or higher, including most commonly (in $>5\%$ of patients), neutrophil count decreased (37 [25.7%] patients), platelet count decreased (32 [22.2%] patients), anemia (25 [17.4%] patients), white blood cell count decreased (21 [14.6%] patients), thrombocytopenia (12 [8.3%] patients), neutropenia (11 [7.6%] patients), hypokalemia (10 [6.9%] patients), and AST increased (8 [5.6%] patients).

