1.2 Potential Risks and Benefits of the Treatment Regimen

Patritumab deruxtecan is being developed for the treatment of HER3-expressing malignant tumors. The product is in the early stages of development.

Nonclinical studies have demonstrated the antitumor activity of patritumab deruxtecan in HER3 tumor-bearing mouse models. Thus, patritumab deruxtecan is hypothesized to demonstrate efficacy in treating HER3-expressing tumors in patients.

Based on the preliminary clinical safety data from the ongoing patritumab deruxtecan studies, nausea, decreased appetite, platelet count decreased/thrombocytopenia, white blood cell count decreased/leukopenia, neutrophil count decreased/neutropenia, vomiting, anemia, diarrhea, fatigue, malaise, stomatitis, constipation, ALT increased, AST increased, and alopecia are identified risks and will continue to be closely monitored and evaluated in the patritumab deruxtecan clinical development program.

Based on clinical data and safety information available as of the 05 August 2019 data cut-off, ILD/pneumonitis was added as an adverse drug reaction associated with the use of patritumab

CONFIDENTIAL

deruxtecan and considered an important identified risk. The reported ILD events were generally manageable via close monitoring and by following the ILD management plan in the protocol.

In conclusion, based on the efficacy and safety data from the nonclinical studies and the preliminary clinical safety data from ongoing studies, the benefit/risk balance supports continued clinical development of patritumab deruxtecan. For more information on the non-clinical and clinical studies, see the current patritumab deruxtecan Investigator’s Brochure (IB).

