1.3 Rationale for the dose

The regimen to be evaluated will be a fixed dose of 5.6 mg/kg administered as a continuous IV infusion on Day 1 of each 21-day cycle.

Data from two studies have been considered for the selection of the 5.6 mg/kg dose. Study U31402-A-J101 included 1.6 mg/kg, 3.2 mg/kg, 6.4 mg/kg and 8.0 mg/kg Q3W in subjects with breast cancer, the MTD was established at 6.4 mg/kg. Study U31402-A-U102 included 3.2 mg/kg, 4.8 mg/kg, 5.6 mg/kg and 6.4 mg/kg Q3W in NSCLC patients, the MTD was established at 5.6 mg/kg. In addition, 4.2 mg/kg every 2 weeks and an up-titration dose regimen were studied in the J101 study, with 3.2 mg/kg in Cycle 1, 4.8 mg/kg in Cycle 2, and 6.4 mg/kg in Cycle 3 and after. Exposure of intact patritumab deruxtecan ADC, total anti-HER3 antibody and released payload MAAA-1181a increased as dose increased. Population pharmacokinetics (PK), and exposure response analyses for efficacy and safety were conducted using data from both the J101 and U102 studies. Exposure-efficacy relationship was established for intact patritumab deruxtecan ADC and the exposure safety relationship was established for released payload MAAA-1181a.

The rationale for the selection of 5.6 mg/kg is based on an exposure-response analysis of efficacy, and 5.6 mg/kg is predicted to provide a lower probability of ≥Grade 3 thrombocytopenia compared to 6.4 mg/kg, and an improved ORR compared to 4.8 mg/kg. More data are being collected in the ongoing patritumab deruxtecan studies to further evaluate this dosing regimen.

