Fatigue/ Asthenia/Malaise	Grade 3	Delay dose until resolved to ≤ Grade 1 or baseline, then: 
 • If resolved to ≤ Grade 1 or baseline in ≤14 days, resume patritumab deruxtecan. • If resolved to ≤ Grade 1 or baseline in >14 days, then reduce patritumab deruxtecan by 1 dose level.
Cardiac disorders		

CONFIDENTIAL

	Worst Toxicity NCI CTCAE Version 5.0 Grade (unless otherwise specified)	Schedule Modification for Patritumab deruxtecan
Heart failure	Grade ≥ 2 (Symptoms with moderate activity or exertion)	Cardiologist consultation as necessary. Delay dose until resolved to \leq Grade 1, then reduce patritumab deruxtecan by 1 dose level.
Ejection fraction decreased	Decrease in LVEF 10% - 20% (absolute value), but LVEF $>45\%$	Continue patritumab deruxtecan.
	LVEF 40% - $\leq 45\%$ and decrease is $<10\%$ (absolute value) from baseline	Continue patritumab deruxtecan. Repeat LVEF assessment within 3 weeks.
	LVEF 40% - $\leq 45\%$ and decrease is $\geq 10\%$ to 20% (absolute value) from baseline	Delay patritumab deruxtecan. Repeat LVEF assessment within 3 weeks. If LVEF has not recovered to within 10% (absolute value) from baseline, discontinue patient from study treatment.
	LVEF $<40\%$ or $>20\%$ (absolute value) drop from baseline	Delay patritumab deruxtecan. Repeat LVEF assessment within 3 weeks. If LVEF $<40\%$ or $>20\%$ (absolute value) drop from baseline is confirmed, discontinue patritumab deruxtecan. Cardiologist consultation as necessary.
Electrocardiogram QT corrected interval prolonged	Grade 3 (Average QTcF ≥ 501 ms; >60 ms change from baseline)	Delay patritumab deruxtecan until resolved to \leq Grade 1 (QTcF ≤ 480 ms). Determine if another medication the patient was taking may be responsible and can be adjusted or if there are any changes in serum electrolytes that can be corrected. If QTcF prolongation is attributed to patritumab deruxtecan, then reduce patritumab deruxtecan by 1 dose level. Cardiologist consultation as necessary.
	Grade 4 (Torsade de pointes; polymorphic ventricular tachycardia; signs/symptoms of serious arrhythmia)	Discontinue patient from patritumab deruxtecan. Cardiologist consultation as necessary.

CONFIDENTIAL

	Worst Toxicity NCI CTCAE Version 5.0 Grade (unless otherwise specified)	Schedule Modification for Patritumab deruxtecan
Respiratory, thoracic and mediastinal disorders		

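### Adverse event tables by preferred term, with no grouped terms, can understate the per-patient incidence of the cytopenias that Section 1.2 treats as single risks

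*Combined protocol and SAP*

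**What the plan says.** Section 10.4.3 (Safety Analysis) codes AEs in MedDRA. The main AE table is to be "summarized using system organ class and preferred term overall and by biomarker-defined subgroup for all patients in the Safety Analysis Set". The section then adds "summaries of SAEs, AEs leading to treatment discontinuation, AEs by maximum NCI CTCAE grade, and AEs related to study treatment", without saying at which term level these are shown. No grouped term, standardized query or composite is named for any AE table. The only MedDRA query in the protocol is in Section 11.4.1, where it triggers data collection for adjudication of interstitial lung disease.

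For laboratory data, the same section plans "A shift table, presenting the 2-way frequency tabulation for baseline and the worst on-treatment value according to the NCI CTCAE grade", plus a listing of results at Grade 3 or above.

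Section 1.2 writes the haematological identified risks as pairs: "platelet count decreased/thrombocytopenia, white blood cell count decreased/leukopenia, neutrophil count decreased/neutropenia". Section 1.1.3 gives the Grade 3 or higher events of the Phase I/II study on separate lines: "neutrophil count decreased (37 [25.7%] patients), platelet count decreased (32 [22.2%] patients" and, further along the same list, "thrombocytopenia (12 [8.3%] patients), neutropenia (11 [7.6%] patients".

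**The concern.** The protocol names each cytopenia pair as one risk to be followed, but the planned AE table has no row for that risk. Section 11.3.1 has AEs recorded verbatim unless they form a recognized diagnosis, so both wordings of one toxicity can reach coding, as the Phase I/II data suggest has already happened with this drug.

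With two rows per toxicity, a reader has two options. Taking the larger row omits anyone who appears only under the other term. Adding the rows double counts anyone who appears under both. Neither is reliably the number of patients affected.

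Safety and tolerability is the first secondary objective. Low platelets matter in particular because Section 1.3 supports 5.6 mg/kg partly on the ground that it "is predicted to provide a lower probability of" Grade 3 or higher thrombocytopenia than 6.4 mg/kg. The trial should be able to state one patient-level AE rate for that risk.

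**Working it through.** **Inputs.** All counts are from the Phase I/II study, with 144 treated patients (Section 1.1.3).

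**Reproducing the stated percentages** (count/144):
- Grade 3+ platelet count decreased: 32/144 = 22.2%; thrombocytopenia: 12/144 = 8.3%.
- Grade 3+ neutrophil count decreased: 37/144 = 25.7%; neutropenia: 11/144 = 7.6%.
- Serious platelet count decreased: 8/144 = 5.6%; serious thrombocytopenia: 4/144 = 2.8%.

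All six match the protocol.

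**Range for the grouped rate.** If *a* patients have one term and *b* the other, the number with either lies between max(*a*, *b*), when everyone with the rarer term also has the commoner one, and *a* + *b*, when nobody has both. The documents give no overlap count, so the whole range is shown. For orientation only, independence of the two terms would give 1 − (1 − *a*/144)(1 − *b*/144).

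| Risk | Larger row | Full overlap | No overlap | If independent |
|---|---|---|---|---|
| Low platelets, Grade 3+ | 22.2% | 32/144 = 22.2% | (32+12)/144 = 30.6% | 28.7% |
| Low neutrophils, Grade 3+ | 25.7% | 37/144 = 25.7% | (37+11)/144 = 33.3% | 31.4% |
| Low platelets, serious | 5.6% | 8/144 = 5.6% | (8+4)/144 = 8.3% | 8.2% |

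So the larger row may miss:
- 0 to 12 patients with Grade 3+ low platelets (up to 12/32 = 37.5% relative);
- 0 to 11 with Grade 3+ low neutrophils (up to 11/37 = 29.7%);
- 0 to 4 with serious low platelets (up to 4/8 = 50%).

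**Any grade.** Thrombocytopenia and neutropenia are absent from the list of events in more than 20% of patients. Since 0.20 × 144 = 28.8, each is at most 28 patients. The grouped any-grade rate is then between 65/144 = 45.1% and (65+28)/144 = 64.6% for platelets, and between 61/144 = 42.4% and (61+28)/144 = 61.8% for neutrophils.

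**White cells.** Section 1.1.3 gives no count for leukopenia, so the size of the effect for the third pair cannot be calculated from the documents.

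**The case against.** **No understatement is shown.** A reader might infer that the planned tables will give figures that are too low. The documents do not establish this: with full overlap, the larger row is already complete. The recording rules do not settle it. Section 11.3.2 has a persistent event entered once but asks for a new entry when its severity changes, so one patient could carry both terms. What stands is that the larger row can be too low, and the tables do not show whether it is.

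**The shift table already counts these patients.** This is the strongest point. The table uses worst on-treatment grade whatever AE term was reported, so it gives a patient-level Grade 3+ count for platelets and neutrophils. It stands in part. The Schedule of Assessments places on-treatment haematology on Day 1 of each cycle, so a fall and recovery between visits appears only if an extra sample was taken. The table also carries no seriousness, relatedness or discontinuation, and no subgroup split is stated for it.

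**Not every AE table is fixed at preferred term.** This is correct. Section 10.4.3 states that level for the main table only. For the serious, related, maximum-grade and discontinuation summaries it is silent, so reading them all as preferred-term tables is an inference. Grouping is still specified for none of them.

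**The data are not lost.** Term, grade, seriousness and causality are all collected, so grouped rates could be programmed later. That is true, but groups chosen after the rates are known are open to the criticism that the results drove them.

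**Conclusion.** The point holds as a gap in how the AE tables are specified. Followed as written, they give no per-patient AE incidence for three risks that the protocol itself defines as pairs. On the Phase I/II counts the possible shortfall is 0 to 8.3 percentage points for Grade 3+ low platelets, 0 to 7.6 for Grade 3+ low neutrophils and 0 to 2.8 for serious low platelets. The upper ends assume that no patient had both terms.

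Two further readings are not supported:
- **Fatigue.** Table 4 has a row for "Fatigue/ Asthenia/Malaise", and a reader might infer the same problem there, with 40/144 = 27.8% becoming as much as (40+31)/144 = 49.3% for fatigue or malaise. That row is a dose-modification entry, and Section 1.2 lists fatigue and malaise as separate risks, so the protocol's risk list does not make this grouping.
- **Projection to this trial.** A reader might scale the platelet rates to 121 patients (121 × 32/144 ≈ 27 against up to 121 × 44/144 ≈ 37). This would borrow rates from a study that spanned several dose levels (1.6 to 8.0 mg/kg in its escalation and dose-finding phases, Section 1.1.4), while this trial starts everyone at 5.6 mg/kg. The figures show how large the effect was in that study; they do not forecast this one.

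The safety analysis is descriptive and the primary endpoints are unaffected. This is a cheap improvement.

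**What to change.** In Section 10.4.3, add a fixed list of grouped terms matching Section 1.2:
- platelet count decreased + thrombocytopenia;
- neutrophil count decreased + neutropenia;
- white blood cell count decreased + leukopenia.

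Count each patient once per group at worst grade. Show the grouped rows in the any-grade, Grade 3+, serious, related and discontinuation summaries, state the term level of each of those summaries, and keep the preferred-term tables as detail. Fix the list before the final analysis. A fatigue/asthenia/malaise group is optional; if it is added, say that it follows Table 4 and not the risk list in Section 1.2.

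The cost is one paragraph, a short term list and a little programming. No new data are needed. The reported rates for these risks may come out somewhat less favourable than the single-term rows.
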